2.8 Combining MR/US-Fusion, hrMRI, and PET-MRI with HIFU for Focal Treatment of Prostate Cancer.....	7
3.0 STUDY DESIGN:	7
3.1 Overview	8
3.2 Study Population	8
3.3 Study endpoints.....	9
3.4 Study Procedures.....	9
3.5 Removal of Subjects from study	13
4.0 Study Risks.....	13
5.0 ADVERSE EVENTS (AE)	14
5.1 Definitions	14

5.2	Reporting Requirements.....	16
6.0	Statistical Analysis.....	17
7.0	STUDY MANAGEMENT	18
8.0	REFERENCES.....	23
9.0	SUMMARY OF CHANGES	25

LIST OF ABBREVIATIONS

AE	Adverse Events
ADC	Apparent diffusion coefficient
AUC	Area under the curve
AS	Active Surveillance
DCE	Dynamic contrast enhanced
DWI	Diffusion-weighted imaging
EPI	Echo-planar imaging
HIFU	High-intensity focused ultrasound
hrMRI	High resolution MRI
mpMRI	Multiparametric MRI
MR/US	MRI-ultrasound
MRI	Magnetic resonance imaging
PET	Positron emission tomography
PI-RAD	Prostate Imaging-Reporting and Data System
PSA	Prostate specific antigen
PSAM	Prostate specific membrane antigen
ROI	Region of interest
SAE	Serious Adverse Events
UTI	Urinary Tract Infection

STUDY SCHEMA

STUDY SUMMARY

Title	High-Resolution, 18F-fluciclovine PET-MRI for Mapping Prostate Cancer in Patients Considering Focal High-Intensity Focused Ultrasound (HIFU) Therapy
Short Title	High resolution PET-MRI before prostate cancer HIFU
Protocol Number	IIT2016-19-[name]-18F
Phase	Phase II
Methodology	Single arm, paired imaging
Study Duration	3 years
Study Center(s)	Cedars Sinai Medical Center
Objectives	To determine if enhanced prostate imaging using two novel imaging technologies (high resolution DWI and 18F-fluciclovine PET-MRI) will detect prostate cancers not seen on standard multiparametric prostate MRI in patients considered candidates for focal HIFU.
Number of Subjects	20 Study Subjects
Diagnosis and Main Inclusion Criteria	
Diagnosis: Clinically localized, unilateral, high-grade prostate cancer OR at high risk for having unrecognized high grade Prostate Cancer
 
Inclusion Criteria:
 
 • Biopsy consisting of ≥ 10 tissue cores sampled • PSA ≤ 20 ng/mL (within 3 months of consent) • cT1-cT2c • Either overall Gleason score ≥ 7 with Gleason grade 4 or 5 component localized to one lobe (i.e. right or left) OR overall Gleason score 6 with \geq half of systematic biopsy cores positive and $\geq 50\%$ of core involvement in at least one core • Patient considering focal HIFU therapy
Study Imaging	18F-fluciclovine PET-MRI in combination with multiparametric prostate MRI using high resolution DWI
Control Imaging	Standard multiparametric prostate MRI
Reference standard	MRI-targeted prostate biopsies will serve as the reference standard and all lesions seen on any MRI protocol will be biopsied.
Statistical analysis	Our hypothesis is that 35% of biopsy-proven tumors will be detected on PET-hrMRI and not on standard MRI. If we assume that no biopsy proven tumors will only be detected on standard MRI, at $\alpha=0.05$, $n=20$ provides a power of 80%.

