We herein propose a prospective trial to evaluate the effectiveness of 18F-fluciclovine PET-hrMRI versus standard mpMRI at identifying prostate cancer targets for HIFU therapy. Patients with clinically localized, unilateral high grade prostate cancer (Gleason score 7-10 prostate cancer localized to one lobe on prior biopsies) OR at high risk for having unrecognized high grade prostate cancer (overall Gleason score 6 with \geq half of systematic biopsy cores positive and \geq 50% of core involvement in at least one core), interested in HIFU would receive both a standard mpMRI and 18F-fluciclovine PET-hrMRI. They would then undergo a mapping biopsy using a standard sextant template plus MRI/US-fusion targeted biopsy of any suspicious lesion on mpMRI or PET-hrMRI. The primary endpoint would assess the number of biopsy-proven cancers that mpMRI would have missed compared with PET-hrMRI. Following our tumor mapping study, patients with high grade disease (i.e. Gleason grade 4 or 5) in one lobe undergo hemigland or focal HIFU of that lobe. At 6 months, patients would undergo repeat prostate biopsy to assess the negative biopsy rate in the treated region and absence of Gleason grade 4 or 5 in the untreated region as secondary endpoints.

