3.1 Overview

This prospective trial will evaluate the effectiveness of 18F-fluciclovine PET-hrMRI versus standard mpMRI at identifying prostate cancer targets for HIFU therapy. Patients with clinically localized, Gleason score 7-10 prostate cancer localized to one lobe on prior biopsies or overall Gleason score 6 with \geq half of systematic biopsy cores positive and \geq 50% of core involvement in at least one core, interested in HIFU would receive both a standard mpMRI and 18F-fluciclovine PET-hrMRI. They would then undergo a mapping biopsy using a standard sextant template plus MR/US-fusion targeted biopsy of any lesions with PI-RADS scores \geq 3 on hrMRI or 18F-fluciclovine PET positivity. The primary endpoint would assess the number of biopsy-proven cancers that mpMRI would have missed compared with hrMRI and/or 18F-fluciclovine PET. Following our tumor mapping study, patients with high grade disease (i.e. Gleason grade 4 or 5) in one lobe undergo hemigland or focal HIFU of that lobe. At 6 months, patients would undergo repeat mpMRI and prostate biopsy (MR/US-fusion biopsy plus standard sextant biopsy) to assess the negative biopsy rate in the treated region and absence of Gleason grade 4 or 5 in the untreated region as secondary endpoints

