3.4.2 Study Calendar

Procedure	Screening	Imaging	Post-imaging²	Standard of Care (SOC) Treatment	Post SOC Treatment 6 months (+/- 1.5 months) following HIFU
Informed Consent/Registration	X				
Demographics/Medical History	X				
Prior and Current Medication Review	X				
Vital Signs ⁵	X				
Physical Exam ⁵	X				
Symptoms Assessment	X				
Standard MRI		X (at least one day prior to targeted prostate biopsy)			X (at least one day prior to targeted prostate biopsy)
			X		X

Tissue collection ⁴					
18-fluciclovine PET-hrMRI		X (at least one day prior to targeted prostate biopsy)			
Adverse Event Review ⁶		X	X	X	X
Hemigland or Focal HIFU ¹				X (performed within 4 months after mapping and/or targeted prostate biopsy)	
Standard Sextant Mapping Biopsy			X		X
MR/US-fusion targeted biopsy			X ³		X

1. Focal HIFU performed on study for patients with confirmed unilateral high grade prostate cancer.
2. End of study for bilateral Gleason ≥ 7 disease
3. Of any lesions with PI-RADS scores ≥ 3 on hr MRI or 18F-fluciclovine PET positivity
4. Tissue collection includes left over tissue from standard of care collection only.
5. Do not need to be repeated if obtained within 90 days of screening.
6. Only grade 3 and above imaging-related AEs will be captured and all SAEs following the receipt of fluciclovine F18.

Pre-HIFU Imaging Protocol for Tumor Mapping

Eligible participants will then undergo mapping MRI in advance of HIFU therapy using both standard mpMRI and PET-hrMRI. All imaging will be completed in one sitting. hrMRI increases the length of the MRI by approximately 5 minutes. PET-MRI sequences increased the length of mpMRI by 30 minutes. Scanning will be done on the Siemens Biograph mMR scanner at the Research Imaging Core facility in the Davis Building.

Subjects undergoing a PET-hrMRI will be screened using the standard clinical protocol to determine whether it is safe to administer contrast to the subject.

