PET scans involve injection of a radioisotope. Subjects undergoing a contrast-enhanced MR-PET will be screened using the standard clinical protocol to determine whether it is safe to administer contrast to the subject. An IV line will be inserted, and the participant will receive 10 mCi $\pm 20\%$ 18F-fluciclovine injection diluted up to 10mL injected via the IV, as an IV bolus injection followed by 10mL flush with normal saline solution. The participant will then be positioned supine in the scanner and will be scanned in the area of the prostate. The research PET scan will be a dynamic list mode scan. Meaning the PET would start first, then 18F fluciclovine would be injected immediately after the scan is started. For the PET acquisition, participants will be imaged for approximately 30 minutes.

All MRI images will be read according to PI-RADS (version 2) by a dedicated GU radiologists who has experience reading over 500 prostate MRIs. All PET scans will be

read by nuclear medicine co-investigators on the study ([name]). All lesions with PI-RADS greater than or equal to 3 and all PET positive areas will be considered suspicious for cancer. A region of interest (ROI) application will be used. The circumference of a suspicious lesion will be drawn on each individual MRI slice. The lesion volume and average ADC will be calculated from the ROI's. The tumor volumes and ADCs will be provided by the radiologist. To prevent the hrMRI from influencing the review of the mpMRI, all mpMRI's will be reviewed first. The radiologist will always be blinded to previous pathology.

Mapping Biopsy Protocols

After the pre-HIFU imaging protocol for tumor mapping, all patients will undergo a transrectal ultrasound-guided targeted mapping biopsy. The biopsy will include a standard sextant template plus MR/US-fusion targeted biopsy of any lesions with PI-RADS scores ≥ 3 on hrMRI or 18F-fluciclovine PET positivity. These areas will be targeted using the UroNav targeting software platform. As an exploratory analysis, remnant formalin-fixed paraffin embedded tumor tissue will be requested for RNAseq transcriptome analysis of lesions that are positive on mapping biopsy.

Eligibility for HIFU

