6.0 Statistical Analysis

Primary Endpoint: To compare the number of biopsy-proven cancers that standard imaging would have missed compared with PET-hrMRI on mapping MRI (i.e. comparison of sensitivity of PET-hrMRI with mpMRI with biopsy-proven cancer as the gold standard).

Our preliminary data suggests that up to 60% of tumors invisible to standard mpMRI are detected on hrMRI. It is unclear how many additional lesions will be identified on fluciclovine PET-MRI. Since all areas of concern will be biopsied and only biopsy-proven tumors will be treated with HIFU, the morbidity of the surgical intervention is minimized and its potential to achieve cure is maximized.

Power Assessment: The power for the McNemar's type test proposed by Durkalski et al. (2003) is evaluated based on four correlations: r1: between lesions evaluated by PET-hrMRI for the same patient, r2: between lesions evaluated by mpMRI for the same patient, r3: between evaluations PET-hrMRI and mpMRI for the same lesion and r4: between evaluations PET-hrMRI and mpMRI for the different lesions at the same patient. In this way, we define four scenarios of correlation among lesions: (a) no correlation ($r1 = r2 = r4 = 0, r3 = 0.15$), (b) low correlation ($r1 = r2 = 0.1, r3 = 0.15, r4 = 0.015$), (c) medium correlation ($r1 = r2 = 0.4, r3 = 0.15, r4 = 0.06$) and (d) high correlation ($r1 = r2 = 0.8, r3 = 0.15, r4 = 0.12$). In addition, the number of lesions for each patient is defined as equal to 1 - 2 on average from preliminary data.

The minimum sample size to reach 80% of power is 22 patients when each patient has exactly 1 lesion (total of 22 lesions); 19 patients when the average number of lesions is 1.35 (total of 26 lesions); and 17 patients when the average number of lesions is 2 (total of 34 lesions). Given that our estimated number of biopsy-proven lesions per patient will be 1–2 based on historical data, we will proceed with a sample size of 20 patients.

Statistical Analysis: Sensitivities will be compared using McNemar's type test proposed by Durkalski et al. (2003) for cluster matched binary data. In addition, the 95% confidence interval for difference between sensitivities will be calculated as proposed by Yang et al. (2012).

Secondary Endpoints: Negative biopsy rate within treatment zones on standard 12-core biopsy 6 months following HIFU therapy; rate of high grade cancer in the untreated lobe.

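### Two conflicting rules for which lesions are targeted at mapping biopsy: under the Section 3 wording, cancers seen only on mpMRI are verified less completely, which biases the primary comparison of sensitivities towards PET-hrMRI

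*Combined protocol and SAP*

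**What the plan says.** **Power.** The Study Summary (Statistical analysis) expects 35% of biopsy-proven tumours to be seen on PET-hrMRI and not on standard MRI. It continues: "If we assume that no biopsy proven tumors will only be detected on standard MRI", 20 gives 80% power at alpha 0.05.

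**Texts that include mpMRI lesions.** The Study Summary (Reference standard) says that "all lesions seen on any MRI protocol will be biopsied". Section 1.0 describes "targeted biopsy of any suspicious lesion on mpMRI or PET-hrMRI". Section 6.0 says that every area of concern is biopsied.

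**Texts that do not.** Section 3.1 limits targeting to lesions with PI-RADS of at least "3 on hrMRI or 18F-fluciclovine PET positivity". Footnote 3 of the Study Calendar (Section 3.4.2) repeats this: "3 on hr MRI or 18F-fluciclovine PET positivity". So does Mapping Biopsy Protocols in the same section: "on hrMRI or 18F-fluciclovine PET positivity. These areas will be targeted using the UroNav targeting software platform". Sections 3.1 and 3.4.2 also give every patient a standard sextant template.

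**Reference standard.** The Study Summary states that "MRI-targeted prostate biopsies will serve as the reference standard". Section 6.0 describes the primary endpoint as "comparison of sensitivity of PET-hrMRI with mpMRI with biopsy-proven cancer as the gold standard", without limiting it to targeted cores. It analyses the endpoint with a McNemar-type test for clustered paired data.

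**The concern.** A McNemar-type test sets cancers seen only on PET-hrMRI against cancers seen only on mpMRI. It is an even comparison only if both kinds of lesion have the same chance of being proven.

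Under the Section 3 wording they do not. A lesion positive only on hrMRI or PET gets targeted cores. A lesion scored 3 or more on mpMRI, below 3 on hrMRI and negative on PET gets none, and depends on a sextant core hitting it. One of the two discordant cells is therefore under-counted, and always in the direction that favours PET-hrMRI.

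The Summary's 0% then cannot be fairly checked against the data, because a low standard-only count could reflect either the imaging or the biopsy rule. What is at stake is the error rate of the primary test if the pilot advantage does not hold.

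**Working it through.** **1. The plan's own figure.** Inputs from the Study Summary: p10 = 0.35 (PET-hrMRI only), p01 = 0 (standard only), alpha = 0.05, taken as two-sided. Normal-approximation McNemar formula, with psi = p10 + p01 and d = p10 − p01:

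n = [1.960·√psi + 0.842·√(psi − d²)]² / d² = 19.89, rounded up to 20.

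Power at n = 20 is 80.3%, so the stated 80% reproduces. By enumeration at 35%/0%, the uncorrected test has 95.6% power and the exact test 75.5%. Power therefore depends on the form of the test, and so do the figures in step 5.

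**2. Does Section 6.0 need the 0%?** Section 2.5 gives pilot sensitivities of 22/23 and 14/23, and Section 6.0 gives r3 = 0.15. If Section 6.0 used these pilot margins (an inference):

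- p11 = 0.9565 × 0.6087 + 0.15·√(0.9565 × 0.0435 × 0.6087 × 0.3913) = 0.597
- p10 = 0.359 and p01 = 0.0115
- the formula in step 1 gives n = 21.5, which matches the 22 patients stated for one lesion each.

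So Section 6.0 appears to work with about 1.2% standard-only, not strictly 0%.

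**3. Where an mpMRI-only lesion goes.**

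| Text | Targeted? | Can it be counted as proven? |
|---|---|---|
| Study Summary, Sections 1.0 and 6.0 | Yes | Yes |
| Sections 3.1 and 3.4.2, any core counts (Section 6.0) | No | Only if a sextant core hits it |
| Sections 3.1 and 3.4.2, only targeted cores count (Study Summary) | No | No |

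**4. Set-up for the size.** Assumptions: 20 true cancers, treated as independent; equal true sensitivities; a share q of cancers seen by each method alone; targeted cores always hit; a share s of untargeted mpMRI-only cancers still proven. The documents give neither q nor s. The discordant counts b (PET-hrMRI only) and c (mpMRI only) have rates q and s·q. The uncorrected test rejects if (b − c)²/(b + c) > 3.84. Section 6.0 does not write out its statistic, so I take this as its single-lesion form.

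At s = 0, c is always 0. The uncorrected test then rejects when b ≥ 4 (16/4 = 4), giving P(Bin(20, q) ≥ 4). The exact test needs b ≥ 6 (2 × 0.5⁶ = 0.031, whereas b = 5 gives 0.0625).

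**5. Chance of a two-sided 5% rejection, by full enumeration.**

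| q each way | s = 1, uncorrected | s = 0.5, uncorrected | s = 0, uncorrected | s = 0, exact |
|---|---|---|---|---|
| 5% | 1.4% | 1.1% | 1.6% | 0.03% |
| 10% | 4.4% | 5.8% | 13.3% | 1.1% |
| 15% | 4.8% | 9.9% | 35.2% | 6.7% |

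At s = 0 every rejection favours PET-hrMRI; the test cannot favour mpMRI.

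**6. What the pilot supports.** hrMRI missed 1 of 23 proven zones, so at most 1 of 23 (4.3%) was seen only on mpMRI. In 20 lesions that is at most 20/23 = 0.87. If the pilot count was 0 of 23, the 97.5% upper bound is 1 − 0.025^(1/23) = 14.8%.

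**The case against.** The strongest reply is that this is loose drafting. Section 3.4.2 itself calls every lesion of PI-RADS 3 or more suspicious, without restricting this to hrMRI, and Section 6.0 has all areas of concern biopsied. Read that way, both groups are verified alike and the bias disappears. That reading may be what was meant. But the narrower rule appears three times in the text that staff will follow: the overview, the calendar footnote and the biopsy procedure. The conflict stands.

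A reader might infer something stronger: that the Section 3 rule itself creates the 0%, so PET-hrMRI sensitivity is 100% by construction. The documents do not support that alone. The same sentences provide sextant cores, and Section 6.0 accepts any biopsy-proven cancer. Exactly 0 requires joining the Summary's reference standard to Section 3's targeting while setting aside the rest of the Summary's own sentence, which has mpMRI lesions biopsied. The s = 0 column is therefore a limiting case.

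Three further points stand:

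- The size depends on the form of the test: 13.3% at q = 10% becomes 1.1% with the exact test.
- The larger figures need q well above the pilot's 4.3%; 15% is just above the 14.8% bound.
- Section 6.0's power does not strictly need 0%.

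They limit the size of the bias but leave its direction unchanged.

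**Conclusion.** The point holds as a contradiction that bears on the primary endpoint. Followed as written, Section 3 verifies mpMRI-only cancers less completely than PET-hrMRI-only cancers and biases the comparison towards PET-hrMRI.

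The size is uncertain. With equal sensitivities and 20 independent lesions, it ranges from none at q = 5% (rejection stays below the nominal 5%) to 35.2% rejection at q = 15%, s = 0 with the uncorrected test. At s = 0.5 the uncorrected test rejects in at most 9.9% over this range. Clustering within patients is ignored.

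If the pilot holds, fewer than one cancer in 20 is affected and the estimate moves little. What is lost is protection against a false positive if it does not hold.

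It would be wrong to infer that 20 patients are too few or that the 80% is miscalculated; it reproduces under its stated assumptions. Nor do the documents show that a positive result is guaranteed.

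**What to change.** - Reconcile the Study Summary, Section 1.0 and Section 6.0 with Sections 3.1 and 3.4.2 (calendar footnote 3 and Mapping Biopsy Protocols), so that one targeting rule applies. Which rule is for the investigators to decide.
- In Section 6.0, state whether cancer found only in sextant cores counts as biopsy-proven.
- In Section 6.0, state that the comparison of sensitivities requires mpMRI-only and PET-hrMRI-only lesions to be verified by the same rule.
- Tabulate every lesion that is PI-RADS 3 or more on mpMRI but negative on hrMRI and PET, with whether it was sampled and the result.
- If the reconciled text does not verify both groups alike, describe the primary result as the added yield of PET-hrMRI, not as a difference in sensitivity.

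The cost is text edits and one table, with no added patients or scans. The possible downside is a more modest conclusion. Depending on the rule chosen, the handling of a few lesions may change at a biopsy already planned: at pilot rates, fewer than one mpMRI-only cancer per 20.

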1.0 STUDY ABSTRACT

The arrival of High-Intensity Focused Ultrasound (HIFU) technology along with advances in prostate imaging may make focal gland ablation feasible. While the mainstays of therapy for clinically localized prostate cancer, surgery and radiation therapy, induce significant morbidity such as urinary incontinence, erectile dysfunction, and bowel dysfunction due to bystander effects of whole-gland treatment, HIFU permits focal destruction of prostate cancers, which has the potential to minimize these morbidities and maximize quality of life. Advances in prostate MRI allow the majority of high grade cancers to be detected. Software platforms exist that enable real-time fusion of prostate MRI images with ultrasound, which allows for targeting of prostate lesions found on MRI during transrectal biopsy. The confluence of all of this technology—HIFU, multiparametric MRI (mpMRI), and MR/US-fusion targeting—creates the possibility of highly targeted focal ablation of prostate cancers. Nonrandomized clinical trials of hemigland and focal ablation with HIFU in Europe have shown promising trilecta rates—cancer control, potency, & continence—up to 1y post-treatment.

While early results of HIFU therapy for clinically localized prostate cancer are promising, the effectiveness of HIFU therapy will ultimately be limited by the accuracy of prostate cancer imaging. Because prostate cancer is often multifocal, identification of all clinically relevant prostate cancer lesions is critical to complete treatment of the disease, whether it is hemigland or true focal ablation. Modern mpMRI is unable to detect 20% of high-grade cancer and approximately 50% of low-grade cancers. To address this shortcoming, our team at Cedars-Sinai has developed high-resolution prostate MRI (hrMRI) technology that improves resolution 5-fold compared with standard multiparametric MRI. (1) High-resolution imaging has been shown to detect 60% of tumors not seen on standard MRI.(2) Pairing this technology with PET may allow highly specific targeting for focal therapy. Because the oncological effectiveness of focal therapy depends on robust targeting, PET-hrMRI could provide a significant advantage in cancer control outcomes for HIFU.

We herein propose a prospective trial to evaluate the effectiveness of 18F-fluciclovine PET-hrMRI versus standard mpMRI at identifying prostate cancer targets for HIFU therapy. Patients with clinically localized, unilateral high grade prostate cancer (Gleason score 7-10 prostate cancer localized to one lobe on prior biopsies) OR at high risk for having unrecognized high grade prostate cancer (overall Gleason score 6 with \geq half of systematic biopsy cores positive and \geq 50% of core involvement in at least one core), interested in HIFU would receive both a standard mpMRI and 18F-fluciclovine PET-hrMRI. They would then undergo a mapping biopsy using a standard sextant template plus MRI/US-fusion targeted biopsy of any suspicious lesion on mpMRI or PET-hrMRI. The primary endpoint would assess the number of biopsy-proven cancers that mpMRI would have missed compared with PET-hrMRI. Following our tumor mapping study, patients with high grade disease (i.e. Gleason grade 4 or 5) in one lobe undergo hemigland or focal HIFU of that lobe. At 6 months, patients would undergo repeat prostate biopsy to assess the negative biopsy rate in the treated region and absence of Gleason grade 4 or 5 in the untreated region as secondary endpoints.

